8.1.3 Withdrawal of Consent

All subjects have the right to withdraw their consent from further participation in the trial at any time without prejudice. Subjects cannot withdraw consent for use of data already collected as

part of the trial, but only for future participation. The investigator can also discontinue a subject's participation in the trial at any time if medically necessary.

Withdrawal of consent is a critical trial event and, therefore, should be approached with the same degree of importance and care as is used in initially obtaining informed consent. The reasons for a subject's intended withdrawal need to be completely understood, documented, and managed to protect the rights of the subject and the integrity of the trial.

Details on the withdrawal of consent from the pharmacogenomic (PGx) assessment and/or optional future biospecimen research (FBR) substudy are provided in the informed consent form (ICF).

8.1.4 Entire Study Termination

The entire study may be suspended or terminated by the Sponsor for safety or other unanticipated reasons or upon request of regulatory agencies. Criteria for premature termination or suspension of the study are detailed in [Section 11.8.1](#).

8.1.5 Individual Study Site Termination

Study participation may be suspended or terminated at an individual investigational site for various reasons. Criteria and procedures for premature termination or suspension of an investigational site are detailed in [Section 11.8.2](#).

8.1.6 Lost to Follow-Up

A subject will be considered lost to follow-up if he or she is unable to be contacted by the study site staff.

The following actions must be taken if a subject fails to return to the clinic for a required study visit:

- The site will attempt to contact the subject and reschedule the missed visit and counsel the subject on the importance of maintaining the assigned visit schedule and ascertain if the subject wishes to and/or should continue in the study.
- Before a subject is deemed lost to follow-up, the investigator or designee will make every effort to regain contact with the subject (where possible, 3 telephone calls and, if necessary, a certified letter to the subject's last known mailing address or local equivalent methods). These contact attempts should be documented in the subject's medical record or study file.
- Should the subject continue to be unreachable, he or she will be considered to have withdrawn from the study with a primary reason of lost to follow-up.
- For subjects who are lost to follow-up, the investigator may search publicly available records to ascertain survival status. This ensures that the data set(s) produced as an outcome of the study is/are as comprehensive as possible.

9.0 STUDY ASSESSMENTS AND PROCEDURES

9.1 General Study Periods

9.1.1 Screening, Enrollment and/or Randomization

9.1.1.1 Informed Consent

Informed consent must be obtained prior to the subject entering into the study and before any protocol-directed procedures are performed (including Screening activities). Additionally, subjects may be asked to provide a separate, optional consent to obtain and store a blood sample(s) for future research.

This study includes 2 screening visits (SV1 and SV2).

9.1.2 Treatment Period

The treatment period of this study includes the following visits:

- A Baseline/randomization visit
- A 52-week treatment period

9.1.3 End of Treatment Visit

Subjects completing the study will undergo a final Week 52 EOT visit according to the SoA ([Section 1.3](#)).

9.1.4 Safety Follow-up

The safety follow-up will be conducted 4 weeks after the EOT visit, or 4 weeks after the last dose of study medication for ET.

9.2 Clinical Assessments

The following clinical evaluations will be conducted during the course of the study. If the evaluations will occur on a hemodialysis day, the clinical evaluations should be completed before dialysis, if applicable.

9.2.1 Medical History, Demographics, and Physical Examination

Medical history, demographic information, and physical examination (including height) will be collected according to the SoA ([Section 1.3](#)). Relevant medical history (with particular emphasis on previous medical conditions that may lead to exclusion) and significant ongoing medical conditions or diseases should be documented.

During the Treatment period, an abbreviated physical examination should be performed at the discretion of the investigator, as clinically indicated.

9.2.2 Vital Sign Measurements

Predialysis temperature, heart rate, blood pressure, respiratory rate, and weight will be assessed in the seated position after 5 minutes of rest prior to blood draws. For blood pressure, a total of 2 measurements at intervals of at least 2 minutes will be performed. Measurements will be taken prior to scheduled blood draws when possible.

Dry weight will be collected for all subjects per site standard of care according to the SoA ([Section 1.3](#)).

9.2.3 Dialysis Adequacy

Dialysis adequacy, as available from local collection, will be recorded in the eCRF.

9.2.4 Dialysis Treatment

Hemodialysis vascular access type use at baseline; and changes in renal replacement therapy (from in-center hemodialysis) throughout the trial.

9.3 Efficacy Assessments

The primary efficacy endpoint is mean change in Hb between Baseline (average pretreatment Hb) and the primary evaluation period (average Hb from Weeks 20 to 26, inclusive). Laboratory evaluations of Hb levels will be conducted according to the SoA ([Section 1.3](#)) and are described in [Section 9.4](#).

9.4 Laboratory and Other Assessments

The following safety and other assessments will be conducted during the course of the study, according to the SoA ([Section 1.3](#)).

Samples for laboratory assays will be sent to a central laboratory for analysis. Detailed instructions for the collection, processing, and shipment of laboratory samples will be provided by the sponsor and the central laboratory. If blood is collected on a hemodialysis day, blood draws should be done prior to dialysis, if applicable. The investigator is responsible for reviewing laboratory results for clinical significance.

Blood samples will be collected for the following laboratory evaluations listed below and will be conducted during the course of the study. For details regarding the timing of these assessments refer to [Section 1.3](#).

- Pregnancy Test: A serum pregnancy test will be performed according to the timepoints in the SoA ([Section 1.3](#)) for females of childbearing potential. Additional serum or local urine (if possible) pregnancy tests may be conducted throughout the study in sufficient number, as determined by the investigator to establish the absence of pregnancy during the study. These results must be available and must be negative before the subject takes the first dose of study medication.
- PK Evaluations (samples to be drawn only for subjects randomized to vadadustat): Plasma samples for PK evaluation will be collected to analyze for both the parent compound

(vadadustat) and its metabolites. Collection time points for PK will be obtained according to the SoA ([Section 1.3](#)). Vadadustat should be dosed prior to the start of dialysis. The predose PK sample should be collected as close to the same time as the serum chemistry sample. Blood samples will be collected and processed according to the Operations/Laboratory Manual. The actual date and time of the PK sample collection will be recorded in the eCRF. Additionally, the time of the dose of trial medication will be recorded in the eCRF and the start and stop time of the dialysis session will be recorded in the eCRF. The date and time of dose and PK samples will be recorded in eCRF.

- After processing into plasma, aliquots will be placed into appropriately labeled tubes and will be placed in a freezer set at -70°C or -20°C , unless otherwise instructed in the Operations/Laboratory Manual. All plasma samples will be shipped to the bioanalytical laboratory for analysis. Information will be provided in the Operations/Laboratory Manual.
- Laboratory Evaluations: Blood samples for laboratory analysis will be obtained according to the SoA ([Section 1.3](#)) and are specified in [Table 3](#).

Table 3 Protocol Required Laboratory Assessments

Complete Blood Count	Iron Indices	Serum Chemistry
Hb hematocrit RBC MCV MCH MCHC platelets RDW Differential WBC • Neutrophils • Lymphocytes • Monocytes • Eosinophils • Basophils	Ferritin Iron TIBC TSAT	Sodium Potassium Bicarbonate Chloride Calcium Magnesium Phosphorus Glucose Creatinine BUN CPK Uric acid Albumin Total Protein
	Lipid Profile	
	Total cholesterol LDL HDL Triglycerides	
	Liver Function Tests	
Additional Laboratory Tests	Total bilirubin ALP ALT/SGPT AST/SGOT LDH	
β-HCG Reticulocyte count ^a Folate Vitamin B12 CRP Erythropoietin		Coagulation Tests^b
		PT PTT INR

β-HCG: beta human chorionic gonadotropin; ALP: alkaline phosphatase; ALT: alanine aminotransferase; AST: aspartate aminotransferase; BUN: blood urea nitrogen; CPK: creatine phosphokinase; CRP: C-reactive protein; Hb: hemoglobin; HDL: high density lipoprotein; INR: international normalized ration; LDH: lactate dehydrogenase; LDL: low density lipoprotein; MCH: mean corpuscular hemoglobin; MCHC: mean corpuscular hemoglobin concentration; MCV: mean corpuscular volume; PT: prothrombin time; PTT: partial thromboplastin time; RBC: red blood cell; RDW: red blood cell distribution; SGOT: serum glutamic-oxaloacetic transaminase; SGPT: serum glutamic-pyruvic transaminase; TIBC: total iron-binding capacity; TSAT: transferrin saturation; VEGF: vascular endothelial growth factor; WBC: white blood cell.

a. An automated reticulocyte count should include both absolute and percent

b. The coagulation tests will be performed for unscheduled visits only.

[REDACTED]

[REDACTED]

[REDACTED]

[REDACTED]

[REDACTED]

[REDACTED]

[REDACTED]

9.6 Pharmacodynamic Assessments

Blood samples for EPO, reticulocytes, and iron indices (ferritin, iron, TIBC, and TSAT) analysis will be collected according to the SoA (Section 1.3). Blood samples will be collected and processed according to the Operations/Laboratory Manual. For all PD sampling, the time of the previous dose of trial medication is to be recorded in the eCRF and the timing of administration of trial medication and the start and stop time of the dialysis session will be recorded in the eCRF.

9.7 Pharmacogenomic Assessments

9.7.1 Pharmacogenomic Samples

A separate informed consent will be required to authorize the collection of PGx samples. PGx samples will be collected from consenting subjects according to the SoA (Section 1.3). Blood samples will be collected and processed according to the Operations/Laboratory manual. The date and time of samples collected for PGx analysis will be recorded. All PGx samples will be shipped to the PGx laboratory for analysis. Information will be provided in the Operations/Laboratory Manual.

[REDACTED]

9.10 Safety and Other Assessments

9.10.1 Adverse Event Assessments

AE collection will begin from time of signing of the Informed Consent Form (ICF) through Safety Follow-up Visit. The investigator and study personnel will review each subject's laboratory and clinical evaluation findings and query the subject directly regarding AEs (see Section 9.11.1.1). Subjects must be followed for AEs until the final required protocol visit or until all drug-related toxicities and SAEs have resolved (or are considered chronic/stable), whichever is later.

9.10.2 Concomitant Medication Recording

All medications (both prescription and non-prescription, and including vitamins, herbals, topicals, inhaled, and intranasal), taken during the screening period and throughout the study, ending at the final protocol required visit, should be recorded on the appropriate eCRF. At each study visit, subjects will be asked whether they have started or discontinued any medication since their previous study visit. This includes single-use or as-needed medication use. All medications and treatments, including vitamin supplements, over-the-counter medications and oral herbal preparations must be recorded in the eCRFs. Heparin injections or saline flushes, are not required to be recorded unless relevant for an AE or SAE, however other concomitant medications administered in the dialysis unit will be recorded. In addition, the ESA, blood transfusion, and iron treatment regimen prior to randomization and date of last dose will be recorded.

9.10.3 Therapeutic Phlebotomy

If a subject's Hb exceeds 14.0 g/dL or the rate of rise of Hb raises concern to the Investigator, the subject may be phlebotomized based on the Investigator's clinical judgment. The method of phlebotomy will be in accordance with the study site's standard clinical practice.

9.11 Adverse Events and Serious Adverse Events

9.11.1 Definitions of Adverse Events and Serious Adverse Events

9.11.1.1 Adverse Events

For the purposes of this study, an AE is any untoward medical occurrence (including an abnormal laboratory finding) that occurs in the protocol-specified AE reporting period; the event does not necessarily have a causal relationship with that treatment or usage.

An AE includes medical conditions, signs, and symptoms not previously observed in the subject that emerge during the protocol-specified AE reporting period, including signs or symptoms associated with pre-existing underlying conditions that were not present prior to the AE reporting period. In addition, any worsening of a pre-existing condition that occurs during the protocol-specified AE reporting period is also considered an AE and will be captured as “worsening” of pre-existing condition

AEs therefore include the following:

- All AEs, whether suspected to be causally related to study medication or otherwise
- All AEs secondary to any medication overdose, medication error, abuse, withdrawal, sensitivity, or toxicity
- Illnesses apparently unrelated to study medication, including the worsening of a pre-existing illness (see paragraph below on Pre-existing Conditions)
- Injury or accidents. Note that if a medical condition is known to have caused the injury or accident (eg, a fall secondary to dizziness), the medical condition (dizziness) and the accident (fall) should be reported as 2 separate AEs.
- Abnormalities in physiological testing or physical examination findings that require clinical intervention or further investigation (beyond ordering a repeat [confirmatory] test)
- Laboratory abnormalities that require clinical intervention or further investigation (beyond ordering a repeat [confirmatory] test) unless they are associated with an already reported clinical event. Laboratory abnormalities associated with a clinical event reported as an AE (eg, elevated liver enzymes in a subject with jaundice) should be described under ‘Comments’ on the report of the clinical event rather than reported as separate AEs.

The following guidelines are to be used when reporting AEs for this study:

Medical Diagnoses – Whenever possible, a medical diagnosis term should be used to report AEs instead of signs and symptoms due to a common etiology, as determined by qualified medical study staff. For example, pneumonia should be the reported AE term, instead of fever and dyspnea, when the diagnosis has been established. Signs and symptoms should be reported as event terms only when the medical diagnosis remains unknown, and revised to a medical diagnosis term once it has been established.

Procedures – Diagnostic and therapeutic non-invasive and invasive procedures, such as surgery, should not be reported as AEs. However, the medical condition for which the procedure was performed should be reported if it meets the definition of an AE. For example, an acute appendicitis that begins during the AE reporting period should be reported as the AE and the resulting appendectomy noted under ‘Comments’.

Pre-planned therapeutic procedures not associated with a new medical condition or worsening pre-existing condition should not be reported as AEs.

Device related events (failures/malfunctions) should not be reported as AEs; however, the etiology or complication associated with the device failure/malfunction should be reported if it meets the definition of an AE.

Pre-existing Conditions – In this study, a pre-existing condition (i.e., a disorder present before the AE reporting period started and noted on the pretreatment medical history/physical

examination form) should not be reported as an AE unless the condition worsens or episodes increase in frequency during the AE reporting period.

Abnormal Test Findings – All laboratory test results will be reviewed by the Investigator. The Investigator will utilize his/her judgment in determining if out-of-range laboratory values are clinically significant and will denote this using the abbreviation “CS” on the laboratory report for source documentation. Laboratory tests that are labeled as clinically significant should be reported as AEs, either separately or as part of a description of a symptomatic AE. If there are significant changes in a laboratory report from a previous visit that are determined to be clinically significant, these should also be reported as AEs. Any abnormal laboratory value which requires treatment or further diagnostic testing and/or results in discontinuation from study should be reported as an AE. An expected laboratory abnormality from a condition that is part of the medical history is not considered clinically significant for the purposes of the study unless it represents a worsening of the condition.

Abnormalities in ALT, AST, and Total Bilirubin – Abnormalities in ALT, AST, and total bilirubin should be reported to the Sponsor’s Medical Monitor or CRO designee within 24 hours of awareness as an SAE with ‘other medically important event’ criteria selected, if the following conditions are met:

- New elevation in ALT or AST $>3 \times$ ULN

If new elevations in ALT or AST $>3 \times$ ULN, **without** an elevation of total serum bilirubin $>2 \times$ ULN are identified, the following steps are to be taken:

- Temporary discontinuation of study medication;
- Repeat testing of ALT, AST, alkaline phosphatase (ALP), and total bilirubin, to be completed within 48 to 72 hours to confirm the abnormalities and to determine trend;
- Study medication should not be resumed until monitoring indicates abnormalities have resolved or are stable.

Details on the management of subjects with other ALT and AST abnormalities are further described in [Section 7.1.3](#).

Worsening of Anemia – In this study, it is possible that some subjects may experience a worsening of anemia. As the primary endpoint of this study assesses Hb response, worsening of anemia is captured as part of this efficacy parameter. Worsening of anemia should not be considered an AE unless the worsening of anemia is associated with a cause *other than* the subject’s CKD.

Transplantation – During this long-term study, it is anticipated that some subjects may receive a kidney transplant. These events will not be recorded as AEs. Subjects will discontinue study medication for receipt of a kidney, other solid organ, hematopoietic stem cell or bone marrow transplant and should continue with the SoA and safety assessments as described in [Section 8.1.2](#).

Malignancy – During this long-term study, some subjects may develop a newly diagnosed malignancy or a recurrence of a malignancy. At the discretion of the Investigator, these subjects may continue study medication. For reporting of AEs of malignancy, see [Section 9.11.1.2](#).

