Of the 2 studies which made up the INNO₂VATE program, the safety data most relevant to this program is the preliminary safety data from Study CI-6548-0017, a study that demonstrated the efficacy and safety of vadadustat compared with darbepoetin alfa for the maintenance treatment of anemia in subjects with DD-CKD. The Conversion and Maintenance Period of this study was from Weeks 0 to 52: conversion to study drug for maintaining Hb (Weeks 0 to 23), primary efficacy period (Weeks 24 to 36), and secondary efficacy period (Weeks 40 to 52).

One thousand seven hundred and seventy-seven subjects were enrolled in the vadadustat arm of Study CI-6548-0017 of which 1768 received vadadustat. Based on these preliminary data, the overall incidence of TEAEs was similar between the vadadustat (88.3%) and darbepoetin (89.3%) comparator arm. Common TEAEs ($\geq 5\%$ for vadadustat-treated subjects) are as below:

Table 2 Treatment-emergent Adverse Events Occurring at $\geq 5\%$ Incidence in Vadadustat-treated Subjects

Preferred Term	Vadadustat	Darbepoetin Alfa
	N = 1768 n (%)	N = 1769 n (%)
Any TEAEs	1562 (88.3)	1580 (89.3)
Diarrhoea	230 (13.0)	178 (10.1)
Pneumonia	195 (11.0)	172 (9.7)
Hypertension	187 (10.6)	244 (13.8)
Headache	160 (9.0)	135 (7.6)
Hyperkalaemia	160 (9.0)	191 (10.8)
Fluid overload	156 (8.8)	173 (9.8)
Fall	150 (8.5)	159 (9.0)
Nausea	149 (8.4)	134 (7.6)
Hypotension	146 (8.3)	141 (8.0)
Vomiting	120 (6.8)	124 (7.0)
Urinary tract infection	110 (6.2)	117 (6.6)
Arteriovenous fistula thrombosis	106 (6.0)	78 (4.4)
Cough	99 (5.6)	121 (6.8)
Dialysis related complication	99 (5.6)	122 (6.9)
Upper respiratory tract infection	99 (5.6)	112 (6.3)
Arteriovenous fistula site complication	94 (5.3)	120 (6.8)
Dyspnoea	92 (5.2)	119 (6.7)
Hypoglycaemia	92 (5.2)	78 (4.4)
Nasopharyngitis	92 (5.2)	84 (4.7)
Pain in extremity	91 (5.1)	117 (6.6)

Source: [Table 14.3.1.2.1](#). Study CI-6548-0017

Drug-related TEAEs were more frequently reported in the vadadustat treatment group (9.6%) than in the darbepoetin alfa treatment group (3.8%). Compared to the 5.3% incidence of Gastrointestinal disorders SOC in the vadadustat treatment group (with the most common TEAEs being diarrhea [2.2%] and nausea [1.5%]), there was a 0.2% incidence of Gastrointestinal disorders SOC with darbepoetin alpha. With the exception of Gastrointestinal disorders SOC, the incidence of drug-related TEAEs is similar between subjects treated with vadadustat (4.2%) and darbepoetin alfa (3.7%).

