9.11.8 Events of Special Interest

The following are considered to be AESIs for this study:

- malignancy including renal cell carcinoma (see [Section 9.11.1.2](#))
- elevation in ALT or AST >3 x ULN (see [Section 9.11.1.2](#))
- hepatotoxicity
- worsening of hypertension
- pulmonary hypertension
- thrombotic events
- congestive HF
- adrenal disorders

Reporting and classification of these events as SAEs (see [Section 9.11.1.2](#)) will be as per usual practice.

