Appendix E. Adverse Events of Special Interest (AESI)

The following items will be presented as AESI.

- Worsening of Hypertension: Hypertension MedDRA SMQ Narrow
- Hepatotoxicity: Drug related hepatic disorders Comprehensive SMQ broad
- Pulmonary Hypertension: Pulmonary Hypertension SMQ narrow
- Adrenal disorder: high-level group term (HLGT) Adrenal gland disorders not elsewhere classified (NEC), high-level term (HLT) Adrenal cortex tests
- Malignancies: Malignant or unspecified tumors MedDRA SMQ broad
- Congestive heart failure: Cardiac failure MedDRA SMQ Narrow
- Adverse event preferred terms used in key queries from FDA briefing document for Roxadustat are listed below:

Medical Topic	PT Term
Thrombosis	Cerebral infarction
	Embolic cerebral infarction
	Ischaemic stroke
	Cerebellar infarction
	Lacunar stroke
	Embolic stroke
	Brain stem stroke
	Lacunar infarction
	Thrombosis in device
	Arteriovenous fistula thrombosis
	Arteriovenous graft thrombosis
	Vascular access site thrombosis
	Vascular graft thrombosis
	Graft thrombosis
	Shunt thrombosis
	Acute myocardial infarction
	Myocardial infarction
	Deep vein thrombosis
	Thrombosis
	Atrial thrombosis
	Peripheral artery thrombosis
	Subclavian vein thrombosis
	Brachiocephalic vein thrombosis

Medical Topic	PT Term
	Subclavian artery thrombosis
	Vena cava thrombosis
	Thrombophlebitis superficial
	Arterial thrombosis
	Thrombophlebitis
	Jugular vein thrombosis
	Venous thrombosis
	Pelvic venous thrombosis
	Venous thrombosis limb
	Cardiac ventricular thrombosis
	Intracardiac thrombus
Device/shunt thrombosis/occlusion/malfunction/Stenosis	Thrombosis in device
	Arteriovenous fistula thrombosis
	Arteriovenous graft thrombosis
	Vascular access site thrombosis
	Vascular graft thrombosis
	Medical device site thrombosis
	Device occlusion
	Arteriovenous fistula occlusion
	Vascular access site occlusion
	Vascular access complication
	Vascular access malfunction
	Arteriovenous graft site stenosis
	Shunt occlusion
	Shunt malfunction
	Vascular graft stenosis
	Anastomotic stenosis
	Vascular access site complication
	Vascular graft occlusion
Device/shunt thrombosis	Thrombosis in device
	Arteriovenous fistula thrombosis
	Arteriovenous graft thrombosis
	Vascular access site thrombosis
	Vascular graft thrombosis

Medical Topic	PT Term
	Graft thrombosis
	Shunt thrombosis
	Medical device site thrombosis
	Device related thrombosis
	Injection site thrombosis
Seizure FDA	Epilepsy
	Epileptic encephalopathy
	Seizure

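### In SAP Appendix E, the composite dialysis-access AESI group omits four terms of the thrombosis-only group and lists two malfunction terms that Protocol 9.11.1.1 keeps out of AE reporting

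*Protocol*

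**What the plan says.** Protocol 9.11.1.1, in its guidance on procedures, tells sites: "Device related events (failures/malfunctions) should not be reported as AEs". The sentence continues with a qualification: "the etiology or complication associated with the device failure/malfunction should be reported if it meets the definition of an AE". Nothing in the protocol exempts dialysis access from this rule. Protocol 9.11.8 lists "thrombotic events" among the events of special interest, but has no item for access malfunction, occlusion or stenosis.

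SAP Appendix E opens with "The following items will be presented as AESI". Part of it is a table of preferred-term groups that the SAP attributes to queries in an FDA briefing document on roxadustat. One group is titled "Device/shunt thrombosis/occlusion/malfunction/Stenosis" and includes "Vascular access malfunction" and Shunt malfunction. Another is titled Device/shunt thrombosis and includes "Device related thrombosis". SAP 6.12.1 builds the AESI summaries from treatment-emergent AEs, so a term can be counted only if a site entered the event as an AE.

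**The concern.** There are two separate problems, both affecting what one AESI row counts.

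First, the composite title begins with device/shunt thrombosis and then adds occlusion, malfunction and stenosis. A reader of the table will expect every subject in the thrombosis-only row to be in the composite row as well. The term lists do not deliver that.

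Second, the SAP plans to count malfunction terms that the protocol tells sites not to enter. A low or zero count for those terms could then reflect the reporting rule rather than the absence of events.

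Every subject in this trial is on in-center hemodialysis, and thrombotic events are a protocol AESI. The access rows will be read, and they should count what their titles say.

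**Working it through.** The plan gives no figure to reproduce here. The check is a term-by-term comparison of the Appendix E lists, followed by a reading of each type of term against the protocol sentence.

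**Step 1: the two lists.**

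| Set | Terms | Number |
|---|---|---|
| In both groups | Thrombosis in device; Arteriovenous fistula thrombosis; Arteriovenous graft thrombosis; Vascular access site thrombosis; Vascular graft thrombosis; Medical device site thrombosis | 6 |
| Composite only | five occlusion, three stenosis, two malfunction and two complication terms | 12 |
| Thrombosis-only group, absent from the composite | Graft thrombosis; Shunt thrombosis; Device related thrombosis; Injection site thrombosis | 4 |

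Composite: 6 + 12 = 18 terms. Device/shunt thrombosis: 6 + 4 = 10. Union: 6 + 12 + 4 = 22.

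**Step 2: when the composite row is the smaller one.** Let S be the number of subjects with at least one of the six shared terms. Among the other subjects, let X be the number with at least one of the 12 composite-only terms, and M the number with at least one of the four omitted terms. The composite row shows S + X and the thrombosis-only row shows S + M. The composite is smaller whenever M > X. Whatever X is, the composite misses every subject whose only device/shunt event is one of the four omitted terms.

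**Step 3: where the omitted terms still appear.** All four are in the Device/shunt thrombosis group. Graft thrombosis and Shunt thrombosis are also in the 34-term Thrombosis group. All treatment-emergent AEs are also tabulated by system organ class and preferred term (SAP 6.12.1). The omission therefore affects the composite row only.

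**Step 4: the 18 composite terms against Protocol 9.11.1.1.**

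| Type of term | Number | Effect of the protocol sentence |
|---|---|---|
| Thrombosis | 6 | Reportable as an etiology or complication |
| Stenosis | 3 | Reportable as an etiology or complication |
| Complication | 2 | Reportable as a complication |
| Occlusion | 5 | Unclear: can be read as a failure or as a complication |
| Malfunction | 2 | Excluded by name; only an identified cause or complication is reported |

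The direct conflict covers 2 of 18 terms and the ambiguity covers 5. A malfunction for which no cause or complication is established has no reporting route. The Schedule of Activities records changes of access type, which would not capture a malfunction of an access that stays in use.

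**Step 5: size.** The documents give no expected incidence for the two malfunction terms or the four omitted terms, so the number of subjects affected cannot be calculated.

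**The case against.** The strongest reply is that little is lost. The protocol sentence does not end at the exclusion, and the same section prefers a medical diagnosis to a sign or symptom. A clotted graft should therefore be entered as a thrombosis. The four omitted terms are reported in their own group. The SAP never says that one group contains the other, and nesting is inferred from the titles. If the lists follow an outside query, keeping them unchanged helps comparison; whether they match that source cannot be checked here. All of this stands, and it limits the point to one row and two terms. It does not remove the mismatch between the composite's title and its content, or the conflict over the malfunction terms.

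A reader might draw three stronger conclusions that the documents do not support:

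- *Access events will be under-counted in general.* Thrombosis and stenosis remain reportable, and the omitted terms are tabulated elsewhere.
- *The fistula thrombosis figures in Protocol Table 2 show what is at stake.* Table 2 gives "Arteriovenous fistula thrombosis" in 106 of 1768 subjects on vadadustat and 78 of 1769 on darbepoetin alfa. That term is in the Thrombosis, composite and Device/shunt thrombosis groups, and neither problem removes it. In the same table, fistula site complication runs the other way (94 against 120).
- *Unblinded sites will label events so as to hide a difference.* Treatment is open-label and the wording leaves room for judgement, but the rule is the same in all arms and SAP 3.5 states a common schedule of visits and assessments. Nothing in the documents shows a differential effect.

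**Conclusion.** The point holds as a minor inconsistency in safety tabulation. The composite group lacks four of the 10 thrombosis-only terms, and two of its 18 terms name events that the protocol keeps out of AE reporting unless a cause or complication is identified. The result is possible under-counting in one descriptive AESI row, of unknown size. The primary efficacy analysis is not touched.

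Two assumptions support this. The composite is taken to be meant to include device/shunt thrombosis in full, as its title suggests. The protocol's word device, which it does not define, is taken to cover dialysis access; Appendix E's own grouping of access terms under device/shunt supports that reading.

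**What to change.** 1. **Appendix E.** Add Graft thrombosis, Shunt thrombosis, Device related thrombosis and Injection site thrombosis to the composite, which takes it from 18 to 22 terms. If the outside query is to be kept verbatim for comparability, say so and also present the union of the two groups. The cost is a list edit or one extra row.

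2. **Protocol 9.11.1.1.** Reconcile it with Appendix E by clarifying to sites that malfunction and occlusion of dialysis access are reported as AEs, with the cause if known. The cost is some extra AE entries. As a protocol change it would also need ethics approval under Protocol 11.2, and if made mid-study it would make ascertainment inconsistent over time.

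3. **If data collection is too far advanced for item 2.** Leave the protocol as it is, footnote the AESI table to say that malfunctions were not collected as AEs, and do not interpret the two malfunction terms. The cost is one footnote.
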